4.2 Scientific Rationale for Study Design

This study is designed to evaluate the safety and efficacy of fixed dose dupilumab (300mg) administered SC every 2 weeks, on top of intranasal corticosteroid spray in participants undergoing sinus surgery for medically recalcitrant nasal polyps in AFRS. The population is composed of participants with ongoing chronic symptoms despite appropriate medical management who elect to undergo sinus surgery per SoC. The randomized, placebo- controlled design allows for determination of IMP efficacy in preventing recurrence of severe sinonasal disease.

The sample size (n=132) and 52-week treatment duration are appropriate to capture maintenance effects while providing 1-year treatment safety data in the intended study population. Following completion of the treatment phase, all participants will enter an additional 12-week observation period to demonstrate durability of response and provide off-treatment safety data.

4.3 Justification for Dose

The dupilumab dose and regimen will be consistent with the product insert for the treatment of nasal polyps, i.e., 300mg by SC injection every two weeks. No dose adjustment for the AFRS nasal polyp endotype is warranted.

4.4 End of Study Definition

The end of study is defined as the last expected visit/contact of the last subject undergoing the study. A subject is considered to have completed the study when he/she has completed their last scheduled visit.

4.5 Treatments administered

4.5.1 Investigational products

Table 4: Investigational study treatments

	Treatment 1	Treatment 2
Treatment name:	Dupilumab	Placebo [^]
Dosage formulation:	150 mg/mL in pre-filled	Pre-filled syringe to deliver
	syringe to deliver 300 mg in 2	2 mL
	mL	
Route of administration:	Subcutaneous	Subcutaneous
Dosage regimen:	Every 2 weeks during	Every 2 weeks
	treatment period	during treatment
		period
Provider:	Sanofi	Sanofi

[^] Placebo contains vehicle and other non-pharmacoactive components contained in Dupilumab IMP

4.5.2 Non-investigational products

All enrolled participants will receive a background of INCS spray and nasal saline irrigations as prescribed by their treating physician per SoC.

4.5.3 Postoperative care

All participants will undergo the following standardized post-operative care:

- Intraoperative packing: hemostatic packing only with either Chitogel, Merogel, Nasopore or PosiSepX dressings. No steroid eluting packing will be used.
- Saline irrigations 2-3 times per day and once or twice daily INCS spray
- Pain medication: at discretion of treating physician
- Oral steroids, prednisone 30 mg x 4 days, 20 mg x 4 days, then 10 mg x 4 days and then stop

Alterations from the above are allowed at the discretion of the treating physician and will be recorded in the study database.

4.6 Preparation/handling/administration/accountability

4.6.1 Preparation and handling

Study drug/placebo will be mailed directly to participants from the study's central pharmacy

Page 18 of 58 Version: 3.7.3 2Apr2024

(Belmar Pharma Solutions, Lakewood, CO). Batch deliveries will occur at three-month intervals and be sent on ice via overnight delivery with temperature monitoring. Injection site and IMP preparation will be completed per product insert and SoC. Site investigators or designees must confirm appropriate storage conditions for all study treatments. Any discrepancies will be reported and resolved prior to treatment administration. Only enrolled participants may receive study treatment.

4.6.2 Administration

The IMP will be administered by licensed study staff at randomization (V3, W0) and study visits V4-6 (W12, 24, 36).

Training of subject/caregiver to complete home administration of IMP will be completed after randomization (V3, W0). Home administration of IMP will be completed during weeks (2, 4, 6, 8, 10, 14, 16, 18, 20, 26, 28, 30, 32, 34, 38, 40, 42, 44, 46, 48, 50) to maintain a 2-week treatment schedule. Patients will receive a total of 26 doses of IMP. Reminder text messages, as well as confirmatory phone calls and used syringe collection will be completed to verify home-administration. Participants who cannot administer at home can come to the clinic for injections.

4.6.3 Accountability

The Sponsor-Investigator is responsible for study treatment accountability, reconciliation, and record maintenance (i.e., receipt, reconciliation, and final disposition records).

A study coordinator at each site will verify patient receipt of all study treatments from the central pharmacy. Delivery confirmations will be automatically stored in the central study database. Additional text reminders, monthly phone calls and collection of IMP will be completed. Coordinators will account for all study treatments, and for appropriate destruction or return of unused treatments. Certificates of delivery, destruction, and/or return should be signed.

External study monitoring will be managed by Westat (Rockville, MD). Specific monitoring activities include the following:

- On-Site Initiation Visit (2-day visit per site)
- On-Site Interim Monitoring Visits (3- day visit, twice a year; five visits per site)
- Ad hoc Remote Interim Monitoring Visits
- On-Site Closeout Visit (2-day visit)

4.7 Randomization and blinding

Randomized participants will be stratified by enrollment site. Randomization will be assigned on a 1:1 basis to treatment group (dupilumab 300 mg every 2 weeks) or placebo. The study data team will prepare a randomization list based on computer-generated random numbers retrieved using a randomization procedure available in statistical packages such as SAS. Block randomization with varying block sizes will be employed to ensure that equal numbers of treatment and placebo participants occur within strata (site) and are balanced with respect to observed and unmeasured baseline factors.

This is a double-blind investigation. Patients, treating physicians and local study personnel will not be aware of cohort allocation.

4.7.1 Unblinding

The study data team will maintain individual treatment codes for each randomized subject. Randomization assignment will only be broken in the setting of a medical emergency, per the discretion of the treating physician, where the appropriate management of the subject requires knowledge of the treatment cohort. This event will be centrally recorded and monitored.

4.7.2 Treatment compliance

The study treatment provided for this study will be used only as directed in this Protocol. The IMP will either be administered at the study site during treatment visits (V3-6) or at home during weeks (2, 4, 6, 8, 10, 14, 16, 18, 20, 26, 28, 30, 32, 34, 38, 40, 42, 44, 46, 48, 50) to maintain a 2-week treatment schedule. Reminder text messages will be sent to all participants the day of a home-administration. Home-administration will be confirmed by recording of both confirmatory phone calls and used syringe collection.

If a home-administered IMP dose is missed and can be given within 7 days from the planned dose date, the IMP should be given. The patient's original schedule should be resumed. If the missed dose is not administered within 7 days, the IMP should not be given. This dose should be designated as a missed dose. IMP will then be given at the next date on the original schedule.

If a treatment visit needs to be rescheduled, the visit must be performed, and the IMP must be administered within 7 days of the original visit window. Investigators should make every effort to assure that no treatment visits are missed during the course of the study. A subject will be discontinued from the study if they miss either two consecutive study visits or IMP doses, or a total of three IMP doses throughout the study period. Any change from the dosing schedule will be recorded.

Investigators should also assure that participants are compliant and on a stable dose of the background INCS spray throughout study period. Any changes to background INCS spray will be recorded for subsequent analysis.

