4.1 Overall Design

This is a multi-center, randomized, double-blinded, placebo-controlled, parallel group study to evaluate the efficacy of dupilumab 300mg administered subcutaneously (SC) every 2 weeks versus placebo in participants with AFRS following planned sinus surgery.

132 participants will be randomized to receive dupilumab 300mg SC or matching placebo while on a background of intranasal corticosteroid sprays twice daily. Patients will be stratified by study site and by baseline comorbid asthma status (yes vs no). ~25% of the randomized participants will have comorbid asthma.

Eligible participants will enter a screening/run-in period on twice daily nasal saline irrigations followed by INCS spray for 2-6 weeks prior to planned sinus surgery. Participants may be consented and enrolled at any time during this 2-6 week run-in period, provided the failure of appropriate medical therapy has been documented as outlined in the inclusion criteria. Eligible participants already on study background therapy for at least two weeks may be consented and enrolled during the pre-surgery period.

Both saline irrigations/INCS and sinus surgery will be completed per standard of care (SoC) and not according to the study protocol. Patients who continue to meet eligibility criteria following surgery will be randomized 1:1 before Visit 3 (Day 0) when they receive placebo or dupilumab 300mg SC every 2 weeks. Patients will receive a total of 26 doses of IMP, via either study

personnel (Visit 3-6 at W0, 12, 24 and 36) or home-administration (W2, 4, 6, 8, 10, 14, 16, 18, 20, 22, 26, 28, 30, 32, 34, 38, 40, 42, 44, 46, 48, 50) to maintain a 2-week treatment schedule. Patient compliance will be recorded via text messages the day of scheduled home administration, as well as monthly phone calls and collection of used syringes during scheduled study visits (Visit 4-7 at W12, 24, 36 and 52). An EOT visit will be conducted at Week 52 (Visit 7). Patients will then be monitored on daily saline irrigation and INCS spray for 12-weeks to evaluate potential disease recurrence after discontinuation of IMP. An EOS visit will be conducted at Week 64 (Visit 8).

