15.3.3 Other Events that Require Accelerated Reporting

The following events are considered Adverse Event of Special Interest (AESI) and require reporting to the sponsor (or designee) within 24 hours of learning of the event:

- Anaphylactic reactions
- Systemic hypersensitivity reactions
- Helminthic infections
- Any severe type of conjunctivitis or blepharitis
- Keratitis
- Clinically symptomatic eosinophilia (or eosinophilia associated with clinical symptoms)
- Pregnancy of a female participant entered in a study as well as pregnancy occurring in a female partner of a male participant entered in the study with IMP;
 - Pregnancy occurring in a female participant entered in the clinical trial or in a female partner of a male participant entered in the clinical trial will be qualified as an SAE only if it fulfills one of the seriousness criteria.
 - In the event of pregnancy in a female participant, IMP should be discontinued.
 - Follow-up of the pregnancy in a female participant or in a female partner of a male participant is mandatory until the outcome has been determined.
 - Abnormal pregnancy outcomes (e.g., spontaneous abortion, fetal death, stillbirth, congenital anomalies, ectopic pregnancy) are considered SAEs.
- Significant ALT elevation
 - ALT >5 × ULN in participants with baseline ALT ≤2 × ULN; OR
 - ALT >8 × ULN if baseline ALT >2 × ULN.
- Symptomatic overdose (serious or nonserious) with IMP or other medication (NIMP)
 - An overdose (accidental or intentional) with the IMP is an event suspected by the Investigator or spontaneously notified by the participant and defined as at least twice the intended dose during an interval of less than 7 days. The circumstances (ie, accidental or intentional) should be clearly specified in the verbatim and symptoms, if any, entered on the AE forms.
 - An overdose (accidental or intentional) with any NIMP is an event suspected by the Investigator or spontaneously notified by the participant and defined as at least twice the maximum prescribed daily dose, within the intended therapeutic interval. The circumstances (ie, accidental or intentional) should be clearly specified.

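### The dosing windows in Table 1 and Section 4.7.2 are not consistent with the IMP overdose definition in Section 15.3.3: a late home dose and an early clinic dose can fall less than 7 days apart

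*Combined protocol and SAP*

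**What the plan says.** Section 4.3 sets the regimen at "300mg by SC injection every two weeks". Section 4.1 states that "Patients will receive a total of 26 doses of IMP", with staff-administered doses at "Visit 3-6 at W0, 12, 24 and 36" and the remainder at home.

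Three rules govern timing:

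- **Clinic visits, Table 1.** The day row carries a window of plus or minus 7 days, so a visit may be early as well as late.
- **Late home doses, Section 4.7.2.** "If a home-administered IMP dose is missed and can be given within 7 days from the planned dose date, the IMP should be given". The next sentence adds: "The patient's original schedule should be resumed". A late dose therefore does not push back the one after it.
- **Rescheduled clinic visits, Section 4.7.2.** Here "the IMP must be administered within 7 days of the original visit window". Read literally, the 7 days run from the window and not from the planned date.

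No section states a minimum interval between two doses. Section 15.3.3 describes an IMP overdose as an event suspected by the investigator or reported by the participant, and "defined as at least twice the intended dose during an interval of less than 7 days". A symptomatic overdose is on the list of adverse events of special interest (AESIs) that must be reported within 24 hours.

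**The concern.** Two 300 mg injections are exactly twice the intended dose. If the timing rules let two injections fall less than 7 days apart, a site can stay within every stated window and still produce what the safety section calls an overdose. Site staff then have two sections that give different signals about the same sequence: one permits the doses, the other classifies the result as a safety event.

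The wording of 4.7.2 also pushes towards giving a late dose, because missed doses count towards discontinuation (4.7.2 and 10.1). Participants hold three-month supplies at home. No section asks staff to check the date of the last home injection before giving a clinic dose. If a participant had symptoms after such a pair, the event would be an AESI and would enter the comparison in Section 14.11.

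**Working it through.** **Inputs**

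- Planned interval: 14 days (4.3).
- Clinic doses: weeks 0, 12, 24 and 36, that is days 0, 84, 168 and 252 (Table 1, 4.1).
- Home doses: the 22 weeks listed in Table 1 and 4.1.
- Home-dose shift: 0 to 7 days late (4.7.2).
- Clinic-visit shift: 7 days early to 7 days late (Table 1).
- Overdose limit: 600 mg in less than 7 days (15.3.3, as 2 × 300 mg).

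**Step 1. Reproduce the plan's own schedule.** 4 clinic + 22 home = 26 doses, each 14 days after the last. This matches 4.1. The home-dose lists in 4.6.2 and 4.7.2 omit week 22 and so give 4 + 21 = 25.

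**Step 2. Formula.** Gap = 14 − (days the first dose is late) − (days the second dose is early) + (days the second dose is late). The smallest gap comes from the latest permitted first dose and the earliest permitted second dose.

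**Step 3. Smallest gap by type of pair, with all windows counted from the planned date**

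| Pair | Calculation | Smallest gap |
|---|---|---|
| Home then home | 14 − 7 − 0 | 7 days |
| Clinic then home | 14 − 7 − 0 | 7 days |
| Home then clinic | 14 − 7 − 7 | 0 days |

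A gap of exactly 7 days is not less than 7, so only the home-to-clinic pairs can meet the definition:

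- Weeks 10 and 12: 70 + 7 = 77 and 84 − 7 = 77.
- Weeks 22 and 24: 154 + 7 = 161 and 168 − 7 = 161.
- Weeks 34 and 36: 238 + 7 = 245 and 252 − 7 = 245.

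The second pair rests on the Table 1 and 4.1 lists. Under the 4.7.2 list the dose before week 24 is week 20, and the smallest gap there is 28 − 7 − 7 = 14 days.

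**Step 4. How large the shifts must be.** The gap is under 7 days when days late plus days early is 8 or more; 4 days late and 4 days early leaves 6. In whole days from 0 to 7 on each side, 1 + 2 + … + 7 = 28 of the 64 combinations qualify. This counts what is permitted. It is not a probability.

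**Step 5. Literal reading of the rescheduling phrase.** The week 12 window is days 77 to 91. Seven days beyond it is 91 + 7 = 98, which is the planned day of the week 14 home dose, so the gap is 0. The same holds for weeks 0/2, 24/26 and 36/38, four clinic-to-home pairs in all.

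**Step 6. When the conflict disappears.** If visits could be late but never early, and the 7 days ran from the planned date, home-to-clinic gaps would be at least 14 − 7 − 0 = 7 days and every pair would clear the limit. That is not what Table 1 and 4.7.2 currently say. It is shown only to locate the conflict, not as a recommended rule.

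**The case against.** **The literal rescheduling route is weak.** The change log for version 3.7.1 describes visits and dosing as allowed within 7 days of the planned date. On that understanding the reference to a window in 4.7.2 is loose wording, and a clinic dose 7 days late still leaves 7 days before the next home dose. This largely stands: the route in step 5 is an ambiguity to clear up, not an established permission. It does not touch the home-to-clinic route, which already counts from the planned date.

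**An early visit after a late home dose arguably does not resume the original schedule.** After a week 10 dose on day 77, the next original date is day 84, and the stated aim is a two-week schedule. This is a fair reading, and the short gap does need two opposite shifts on one pair. But neither Table 1 nor 4.7.2 bars an early visit after a late home dose, and the two-week phrase states an aim without a limit. The conflict stays open on the text.

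**The overdose text is a reporting definition, not a dosing rule.** True, and only symptomatic overdoses are AESIs. A reader might infer that the 14.11 comparison is distorted. The documents do not support that: the same windows apply to both arms, and no frequency or difference between arms is shown.

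**Controls exist.** Section 4.7.2 requires changes from the dosing schedule to be recorded, and there are reminder texts, phone calls and syringe collection. So it would be wrong to infer that such pairs go unrecorded. What is missing is any statement that an in-window short gap is a deviation, or any check of the interval before a clinic dose.

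**Conclusion.** Wrong as written; should be fixed. The windows in Table 1 and 4.7.2 permit a home-to-clinic gap of anything from 14 days down to 0, and any gap under 7 days meets the protocol's own overdose definition. Three pairs per participant are affected (weeks 10/12, 22/24 and 34/36, the second only if week 22 is a dosing week). Four clinic-to-home pairs are added only if the rescheduling phrase is taken literally.

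This rests on two assumptions: that an early visit within the Table 1 window may include the dose, and that a preceding late home dose does not restrict it. Nothing in the documents says otherwise.

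A reader might take 28 of 64 as meaning that short gaps will be common, or conclude that every pair of doses is at risk. Neither follows. The count describes permitted combinations only, and two consecutive home doses cannot be less than 7 days apart under 4.7.2.

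**What to change.** Reconcile the Table 1 visit window, the dosing rules in 4.7.2 and the overdose definition in 15.3.3, so that no in-window sequence of two doses meets that definition. In 4.7.2, use one anchor for rescheduled clinic doses, either the planned date or the window. How this is achieved is the sponsor's clinical decision, and no particular dosing rule is proposed here. The week 22 entry should be made the same in Table 1, 4.1, 4.6.2 and 4.7.2 at the same time, because it decides whether the weeks 22/24 pair exists.

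The cost is a short protocol wording change. The downside is small: a few doses may have to be re-timed or counted as missed, and missed doses count towards discontinuation under 4.7.2, so the sponsor should look at that consequence when choosing the wording.

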Participants will return to their respective study site for dosing visits (Visit 3-6), EOT and EOS for evaluation of efficacy and safety. Collection of optional blood and nasal secretions for exploratory biomarker analysis will be completed at study visits 1, 3, 4, 5, 7 and 8. Nasal polyp tissues will be collected at time of surgery (Visit 2).

Sinus surgery will be completed per SoC. Study protocol will determine cohort assignment (use of IMP versus placebo) with all other SoC interventions allowed throughout the entire study. Physician prescribed SoC medications for the treatment of nasal polyps include INCS sprays and nasal saline irrigations. Rescue medications are allowed per the treating physician's discretion.

Rescue medications (topical/oral corticosteroids, topical/oral antibiotics, or revision sinus surgery) will be allowed as deemed clinically necessary for the treatment of an acute exacerbation of CRS (AECRS) by the treating physician. See Table 3 for standardized criteria to diagnose AECRS [1]. If at any point a subject meets discontinuation criteria, an early discontinuation visit will be performed (see Section 8.1- Discontinuation of study treatment).

Table 3: Diagnostic Criteria for AECRS

- Duration of symptoms ≥7 days
- Total SNOT-22 score increased >9 from baseline
- Objective evidence of sinonasal inflammation by nasal endoscopy or CT scan

AECRS; Acute exacerbation of chronic rhinosinusitis

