10.1 Discontinuation of study treatment

Participants may be discontinued from study treatment under the following circumstances:

- Subject decision. Participants may discontinue treatment at any time
- AE that, in the opinion of the Investigator, contraindicates continuation.
- Pregnancy
- IMP unblinding
- Development of any study specific criteria for discontinuation:
 - Anaphylactic reaction to the IMP requiring epinephrine
 - Helminth parasitic infestations requiring hospitalization
 - If 2 consecutive study visits or 2 doses of IMP are missed during the course of the study

All participants who discontinue treatment should remain enrolled and complete their discontinuation visit within 8 weeks of last IMP. At that visit, although no longer receiving IMP, participants should be encouraged to complete all subsequent study visits and procedures. Data collection should continue according to the study protocol.

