15.3 Recording and Reporting Adverse Events

See Section 10.1- Discontinuation of study treatment for safety criteria resulting in study discontinuation.

Recording and reporting will be performed from the time the informed consent is signed until the EOS. The Participants or their legally authorized representative will report adverse events to the investigator or trained members of the study team.

The investigator is responsible for detecting, evaluating, recording, and evaluating all events that meet the definition of AEs and SAEs, by following the following steps:

- Review all documentation related to the event, including symptoms, clinic progress notes, laboratory reports, and diagnostic reports,
- Attempt to establish a diagnosis of the event and document as the AE /SAE
- Record the AE/SAE on the CRF
- Report to the sponsor

The investigator will also be reporting and following up with the events related to the study intervention or that caused the participant to discontinue the intervention.

The follow-up consists of further tests and examinations (laboratory, histopathological, consultation with other healthcare professionals) to demonstrate the nature and/or causality of the AE/SAE.

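### Section 4.7.2 removes participants from the study for missed doses or visits where Section 10.1 stops study treatment only; followed literally, 4.7.2 could lose week-52 data that the treatment-policy estimand uses

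*Combined protocol and SAP*

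**What the plan says.** Section 4.7.2 (Treatment compliance) sets the missed-dose rule for home injections: "If the missed dose is not administered within 7 days, the IMP should not be given". It then gives the consequence of repeated misses: "A subject will be discontinued from the study if they miss either two consecutive study visits or IMP doses, or a total of three"; the sentence goes on to make clear that the three are doses, counted over the whole study period.

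Section 10.1 is headed as discontinuation of study treatment and opens: "Participants may be discontinued from study treatment under the following circumstances". One listed circumstance is: "If 2 consecutive study visits or 2 doses of IMP are missed during the course of the study". It then says what follows: "All participants who discontinue treatment should remain enrolled and complete their discontinuation visit within 8 weeks of last IMP", and "participants should be encouraged to complete all subsequent study visits and procedures. Data collection should continue according to the study protocol".

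Two other places point towards these rules. Section 4.1 says: "If at any point a subject meets discontinuation criteria, an early discontinuation visit will be performed (see Section 8.1- Discontinuation of study treatment". Section 15.3 says: "See Section 10.1- Discontinuation of study treatment for safety criteria resulting in study discontinuation".

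Section 14.6 makes week 52 the primary ITT test and handles treatment discontinuation by a treatment-policy strategy, so data obtained after stopping treatment enter the analysis. Section 14.8 fills missing values by multiple imputation. Footnote a of Table 1 gives early discontinuers an assessment as soon as possible with the end-of-treatment procedures.

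**The concern.** The two sections give a site different instructions for the same event. A participant cannot be both taken out of the study and kept enrolled for all later visits.

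The choice affects the estimand. A treatment-policy estimand needs outcomes after treatment stops, and 14.6 commits to using them. If follow-up ends when adherence fails, the week-52 mLK score and the later oral corticosteroid record of those participants are never collected. The analysis then depends on a model for the outcomes of non-adherent people. Data not collected at the time cannot be recovered later.

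**Working it through.** **1. The two rules side by side**

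| | Section 4.7.2 | Section 10.1 |
|---|---|---|
| Visit trigger | two consecutive | two consecutive |
| Dose trigger | two consecutive, or three in total | two; not clear whether *consecutive* carries over from the visits |
| Force | will | may |
| What stops | the study | study treatment |
| Follow-up | not mentioned | stays enrolled, later visits encouraged, data collection continues |

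The firm differences are study versus treatment, *will* versus *may*, and the three-dose total. The dose counts diverge under either reading of 10.1. If *consecutive* does not carry over, two scattered misses trigger 10.1 but not 4.7.2. If it does, three scattered misses trigger 4.7.2 but not 10.1.

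**2. Does another section settle it?**

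- Section 4.1 refers to an 8.1 on discontinuation of study treatment. Section 8 is now the local number of participants, so the pointer is stale. Its title suggests that 10.1 is meant.
- Section 15.3 cites 10.1 by its treatment-discontinuation title but describes the result as study discontinuation, which blurs the two terms.
- The Study Summary (posttreatment period) names stopping IMP early and discontinuing from the study as separate events, so a literal reading of 4.7.2 is reasonable. It asks both groups back for the last scheduled visits without saying which visits those are.

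None of these ranks one rule above the other.

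**3. Who is exposed, and when**

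Inputs: doses at W0, W2, ..., W50 (Section 4.1), which is 50/2 + 1 = 26; W0 taken as received, because Section 7 defines randomized participants as having received IMP; a home dose counts as missed once 7 days have passed (4.7.2).

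- Earliest dose trigger: W2 and W4 missed. W4 + 1 week = W5, with all five later visits (W12, 24, 36, 52, 64) still ahead.
- Three-dose rule: 26 - 3 = 23 doses, and 23/26 = 88.5%. A participant who took up to 88% of doses could meet it.
- Late triggers: used syringes for W38 to W50 are collected at the week-52 visit, so a late miss may be found only there, unless a monthly call finds it first. If W46 and W48 are missed, the last dose was W44, and the 10.1 deadline for the discontinuation visit is 44 + 8 = W52. That visit may itself fall in the week-52 window.
- Visit trigger: someone who misses two consecutive visits may already be lost to follow-up under 10.2, so the wording changes less there.

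The avoidable loss is therefore mainly among participants who miss doses, still attend visits, and are identified well before week 52.

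**4. The plan's sample size**

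Inputs from 14.1: difference 2, SD 3.5, two-sided 0.05, 66 per group.

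- Standard error = 3.5 x sqrt(2/66) = 0.609; noncentrality = 2/0.609 = 3.28.
- Two-sample t-test power: 90.3% at 66 per group and 89.9% at 65. The stated 90% reproduces, and 66 is the smallest number that reaches it.
- 2 x 66 = 132, the number to be randomized, so nothing is added for attrition.

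**5. What cannot be computed**

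The documents give no missed-dose rate, no expected attrition, no outcome assumption off drug, and no list of variables for the imputation model. The number affected, the power lost, and the size and direction of any bias do not follow from them.

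**The case against.** The strongest reply is that 4.7.2 is one loosely worded sentence in a section on compliance, while 10.1 is the dedicated discontinuation section. Section 10.1 is explicit on retention and agrees with 14.6. Section 15.3 shows that the authors use the two terms interchangeably, and the Study Summary calls even study discontinuers back for visits with endoscopy. Reminders, monthly calls, the 7-day make-up window and clinic injections all limit how often the dose trigger is met.

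Most of this stands: 10.1 is probably what was meant, and exposure is limited. It does not remove the conflict. Section 4.7.2 is mandatory where 10.1 is permissive, it is where a coordinator would look after a missed dose, and no text says that 10.1 prevails. The Study Summary call-back does not clearly secure a week-52 assessment.

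A reader might also infer that removal under 4.7.2 must always come before the week-52 assessment. The documents do not support that. Meeting a trigger is not the same as the site detecting it, as the W38 to W50 syringes show. The W50 dose may also be given up to day 350 + 7 = 357, which is the day the week-52 window opens (364 - 7 = 357). Nor can one say that the early discontinuation visit is never a week-52 value.

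**Conclusion.** The inconsistency is certain and can be read in the current text. Its consequence is conditional: if a site follows 4.7.2 literally, later mLK and oral corticosteroid data, including week 52, may not be collected for participants who miss doses but still attend. Those data would be imputed, contrary to the treatment-policy strategy in 14.6. This rests on the site acting on 4.7.2 over 10.1, and on the trigger being detected well before week 52.

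A reader might infer a stated loss of power or a bias in the week-52 contrast. Any such figure would need a loss rate and an off-drug outcome that the documents do not give, so none is offered. The absence of an attrition reserve means that lost values are not cushioned by design, but it does not say how many would be lost. Nor do the documents show that data will be lost. The point is worth correcting because the plan's own estimand depends on the follow-up that 4.7.2 would end.

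**What to change.** - In 4.7.2, replace *from the study* with *from study treatment (IMP); see Section 10.1*.
- Use one missed-dose and missed-visit trigger in both sections. Which count is clinically right is for the investigators to decide.
- State that scheduled visits, endoscopy recordings, and the recording of oral corticosteroid use and surgery continue through weeks 52 and 64 unless consent is withdrawn.
- Correct the stale Section 8.1 reference in 4.1, and use the same term in 15.3.

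The cost is a short amendment and a few more off-treatment visits, which 10.1 already foresees. Sample size and analysis do not change.
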